5.5 Risks and Anticipated Adverse Device Effects

Potential risks associated with Achilles infusion set use and/or extended wear include but are not limited to the following:

Infusion Site Reactions:

- Localized pain
- Bleeding
- Bruising
- Induration
- Infection
- Itching/ Pruritus
- Purulence
- Reddening (erythema)
- Swelling

- Other
- Non-specified irritation

Infusion Set Issues:

- Infusion Set Failure
- Infusion Pump Failure
- Infusion pump dosing error

Achilles Device Related Risks:

- Cannula Kinking
- Insulin leak from site
- Insulin leak from set or tubing
- Adhesive failure
- Cannula dislodgement
- Cannula insertion failure (not all holes below epidermis)
- Incomplete tubing prime
- Incomplete cannula prime
- Air Bubbles in tubing
- Defective venting in insulin pump / reservoir / infusion set connection

The primary risks associated with extended wear of the Achilles infusion set are increased risk of hyperglycemic or hypoglycemic episodes and/or infusion site irritation or infection. To ensure patient safety while using the newly developed infusion sets, patients are required to wear a Dexcom G5 CGM sensor throughout the study.

Failure of the investigational Achilles infusion set may occur during the 7-day extended wear period. However, if Achilles infusion set failure occurs at any time during the home wear period, the subject will simply be instructed to change out the investigational device for their standard commercially available set to maintain CSII therapy. This is the same risk associated with a use of commercially available infusion sets.

6 Study Design

6.1 General

6.1.1 Study Type and Rationale

This is a prospectively enrolled, non-randomized feasibility study of device performance, tolerability and safety of the investigational Achilles infusion set during two 7-day home use periods. This study has been designed to mimic other studies of insulin infusion set functionality and infusion site reactions, and to collect early human data using the Achilles infusion set (cannula) design and feasibility for extended wear periods.

6.1.2 Measures to Minimize Bias

This study is designed as a single arm device feasibility evaluation. All eligible patients who complete informed consent shall be considered for study participation. No randomization is required. Due to the nature of the disease state and to minimize unknown effects of extended wear of an infusion set, only adult patients will be considered for study participation. Female patients who are pregnant or nursing shall be excluded from the study. To maintain consistent insulin kinetics and blood glucose monitor, participants will be provided with the same insulin analog during the study, study assigned blood glucose and ketone monitors and test strips for study duration. Participants will independently record any device issues, skin irritation or other adverse events that occur during routine home wear and therapy.

6.1.2 Primary Endpoint

Week 2 and Week 3:

The primary endpoint of this study is Insulin delivery through the Achilles infusion set cannula, as evidenced by the absence of uncontrolled hyperglycemia/suspected occlusion, defined as:

The occurrence of unexplained hyperglycemia (glucose >250 mg/dL or 14 mmol/L) occurring more than 2 hours after a meal and not responsive to a pump bolus dose where response to the bolus is defined as a fall of at least 50 mg/dL (3 mmol/L) in blood glucose within one hour, or

- The occurrence of any hyperglycemic episode (glucose >250 mg/dL or 14 mmol/L) not associated with acute intercurrent illness, but with a concurrent ketone level ≥ 0.6 mmol/L.

Other evidence of infusion set failure includes:

- Signs of infection (e.g. erythema or induration >1 cm in maximal diameter), or
- occurrence of a non-resolvable insulin pump occlusion alarm signal

***NOTE:** Cannula function criteria refer to hyperglycemic episodes that participants recognize and attempt to correct with an insulin bolus or document with ketone elevation. Participants may take SMBG measurements in case of unexplained hyperglycemia or if for any other reason the subject questions the CGM readout.*

Week 1:

The primary endpoints for Week 1 of this study are the following:

- Cannula dislodgement from subcutaneous space (with or without liquid leakage at the cannula infusion site), or
- other Achilles device malfunction (e.g., inability to pierce skin, bending, kinking or other malformation that might impact insulin infusion, securement failure).

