5.4 Intended Performance/Success Criteria

Results of this study will be compared to those of Patel et al. (3), who observed that 30% of infusion sets performed adequately (no premature failure due to mechanical malfunction and no episodes of uncorrectable hyperglycemia prior to the end of 7 days of infusion set wear time), and, among infusion sets that did not exhibit mechanical malfunction, 60% performed adequately by the glucose control metrics for the 7-day wear period. Success criteria will be considered met if the Achilles infusion set exceeds these performance outcomes.

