6.1.3 Secondary Endpoints

The secondary endpoints of this study include:

- Achilles infusion set device function as evidenced by the absence of device failure with or without uncontrolled hyperglycemia. Device failure is defined as:
 - Cannula dislodgement from subcutaneous space (with or without liquid leakage at the cannula infusion site), or
 - other Achilles device malfunction (e.g., inability to pierce skin, bending, kinking or other malformation that might impact insulin infusion, securement failure).

SEE ABOVE NOTE
- Standard glucose control measures obtained from Continuous Glucose Monitoring, including observed hyper- and hypoglycemic episodes.
- Subject tolerability levels for the initial manual Achilles infusion set insertion, daily wear and final removal will be assessed using a visual analog pain scale (VAS).
- The incidence, seriousness and potential relationship infusion site to the investigation device of all adverse events will be documented and reported.

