7.2 Populations for Analysis

Intent-to-Treat (ITT) Analysis Population: All participants who meet all eligibility criteria and have undergone a first attempt to insert an investigational Achilles infusion set shall be included in the ITT analysis population.

Safety Analysis Population: All participants who had an investigational cannula inserted.

Per-Protocol (PP) Analysis Population: All patients who completed any part of the 7-day Achilles infusion set evaluation period.

The primary effectiveness analysis will be based on the ITT subject population. Sensitivity analyses of the primary effectiveness endpoint will be generated based on the PP population. The ITT population may contain some patients who did not complete the evaluation interval. This will require the use of imputation methods for missing values. Last observation carry forward will be used in such case.

The primary safety analysis will be based on the safety population. All secondary and exploratory effectiveness analyses will use both the ITT and PP populations.

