7.3 Analysis of the Primary Efficacy Endpoint

The primary study endpoint is the proportion of Achilles infusion sets that function each day of use, up to 7 days. This endpoint will serve as both the preliminary effectiveness and safety endpoint during the feasibility evaluation.

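### The 30% benchmark counts mechanical malfunction as failure, the Weeks 2-3 primary endpoint does not, and no endpoint or analysis section specifies the matching composite

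*Combined protocol and SAP*

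**What the plan says.** **Success rule.** Section 5.4 takes two figures from a published infusion-set trial. In the first, 30% of all sets were adequate, meaning "no premature failure due to mechanical malfunction and no episodes of uncorrectable hyperglycemia prior to the end of 7 days" of wear. The second is conditional: "among infusion sets that did not exhibit mechanical malfunction, 60% performed adequately by the glucose control metrics for the 7-day wear period". Then: "Success criteria will be considered met if the Achilles infusion set exceeds these performance outcomes". Section 5.3 sets no statistical hypothesis, so this is the only success statement in the plan.

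**Primary endpoint, Weeks 2-3.** Section 6.1.2 (Primary Endpoint) defines insulin delivery "as evidenced by the absence of uncontrolled hyperglycemia/suspected occlusion" by two glucose-based criteria: no response to a bolus, or raised ketones. It adds infection signs and a non-resolvable occlusion alarm as other evidence of failure. The failure list in section 1.4.1 has the same four items.

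**Mechanical failure.** Dislodgement, kinking, inability to pierce skin and securement failure are primary only for the saline week. For the insulin weeks they belong to a secondary endpoint in 6.1.3: "Achilles infusion set device function as evidenced by the absence of device failure with or without uncontrolled hyperglycemia". Section 6.1.4 collects the number of failures under both 6.1.2 and 6.1.3.

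**Analysis.** Section 7.3 states: "The primary study endpoint is the proportion of Achilles infusion sets that function each day of use, up to 7 days". It adds: "This endpoint will serve as both the preliminary effectiveness and safety endpoint during the feasibility evaluation". It does not say whether a set with a 6.1.3 failure still functions, and nothing in section 7 links an analysis to 30% or 60%.

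**The concern.** The benchmark and the stated primary endpoint differ in what they count as failure. The words *with or without* in the 6.1.3 definition show that the protocol itself expects some mechanical failures without uncontrolled hyperglycemia. Under 6.1.2 alone such a set is a success. Under the benchmark's definition it is a failure.

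Mechanical reliability is central to the device's rationale: sections 4.2 and 4.7 present kink resistance as its advantage. The 60% criterion cannot make up for the omission, because it is computed only among sets that did not malfunction mechanically. The composite could be rebuilt later from the listings in 7.7, but the scoring rule would then be chosen with the results in view.

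**Working it through.** The plan has no power calculation or error rate to reproduce. The check asks how often a device that exactly equals the benchmark would be declared successful under each scoring.

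**Inputs from the documents.** Benchmarks of 30% and 60% (5.4); 20 participants (6.2.6), each with two insulin-week sets, so at most 40 sets.

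**Assumptions.** The 30% and 60% come from one set of devices with a common denominator. Sets are independent. A share *s* of mechanical failures also meets a 6.1.2 criterion. The documents do not give *s*, so it is varied.

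**Step 1: implied mechanical malfunction.** Share free of malfunction = 0.30 / 0.60 = 0.50, so malfunction = 0.50. If both figures were rounded to whole percents, the range is 1 − 0.305/0.595 = 0.487 to 1 − 0.295/0.605 = 0.512. A benchmark-equal device therefore has 0.30 adequate sets, 0.50 × 0.40 = 0.20 glucose-only failures and 0.50 mechanical failures.

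**Step 2: apparent success on 6.1.2 alone.** Rate = 0.30 + 0.50 × (1 − *s*).

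**Step 3: probability of success.** Exceeding 30% of 40 sets means at least 13, from the exact binomial. Meeting both criteria uses the exact multinomial: (adequate + silent mechanical)/40 > 0.30 and adequate/(adequate + glucose-only) > 0.60.

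| Scoring | Apparent rate | P(>30%) | P(>60%) | P(both) |
|---|---|---|---|---|
| Matched composite (*s* = 1) | 30% | 0.42 | 0.49 | 0.34 |
| 6.1.2 only, *s* = 0.9 | 35% | 0.69 | 0.49 | 0.44 |
| 6.1.2 only, *s* = 0.75 | 42.5% | 0.93 | 0.49 | 0.485 |
| 6.1.2 only, *s* = 0.5 | 55% | 0.999 | 0.49 | 0.488 |

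**Step 4: sensitivity.**
- Rounding of the benchmarks moves the matched P(both) to 0.33-0.35 and its ceiling to 0.47-0.51.
- With 36 sets (illustrative), P(both) is 0.40 matched, 0.46 at *s* = 0.9 and 0.49 at *s* = 0.75. The gap narrows because the cut-off becomes 11/36 = 30.6% instead of 13/40 = 32.5%.
- The 60% criterion hardly reacts to mechanical performance. With 60% glucose success among intact sets, P(>60%) is 0.49, 0.49 and 0.48 at 30%, 50% and 70% malfunction (illustrative rates).

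**Step 5: infection runs the other way.** It is a failure in 6.1.2 but is absent from the benchmark as 5.4 words it. Suppose 5% of sets (assumed) are infection-only removals that would otherwise be adequate. Matched P(both) is then 0.11 if they count as failures in both comparisons, 0.21 if they are excluded from both, and 0.34 if they count as adequate. At an assumed 1.5% the figures are 0.26, 0.31 and 0.34.

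**The case against.** The strongest reply is that 5.4 already words the composite when it describes the benchmark. Asking Achilles to exceed those outcomes most naturally means measuring the same outcomes on Achilles. Section 6.1.4 collects both failure types, and 6.1.3 uses the word *function*, which 7.3 then uses. This stands in part. A reader might infer that the plan directs a comparison of the 6.1.2 rate with 30%, or that the composite appears nowhere. The documents support neither. They leave the comparison unspecified while naming a primary endpoint that does not match.

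The effect on the overall decision is also limited. Success needs both criteria, and the 60% criterion caps the joint probability at about 0.49. This stands too, as does the point that a 20-person feasibility study with no hypothesis makes no confirmatory claim.

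A reader might further infer that the rule in 7.2, "Last observation carry forward will be used in such case", would carry a silently dislodged set forward as functioning to Day 7. Week 2 ends only on an infusion set failure or after 7 days, so the text permits that reading. It does not compel it. Section 6.1.4 labels 6.1.3 events as infusion set failures, 2.9 allows for a Week 2 wear period that ends early, and a recorded device failure is an observed event, not a missing value. No weight is placed on this route.

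Finally, counting infection-only removals as failures would itself depart from a like-for-like comparison. That is correct, and Step 5 shows that the choice can matter as much as the mismatch.

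**Conclusion.** The mismatch is in the text and should be fixed. The stated Weeks 2-3 primary endpoint omits failures that the 30% benchmark counts, and no endpoint or analysis section says which proportion is to be compared with 30%. Using the primary endpoint as written would favour Achilles, unless infection-only failures offset the effect.

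The 30% criterion could lose most of its meaning if a quarter or more of mechanical failures were silent. The joint decision moves less, by 0.10 at *s* = 0.9 (0.44 − 0.34) and by about 0.15 at most (0.49 − 0.34). It would be wrong to conclude that overall success becomes near-certain.

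The direction follows from the definitions. The size rests on an unknown silent share, a common denominator for the two benchmarks, and independence of two sets per participant.

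**What to change.** 1. In 5.4 and 7.3, state that the figure compared with 30% is the Weeks 2-3 proportion of sets that reach Day 7 with no 6.1.3 device failure and no uncontrolled hyperglycemia or suspected occlusion under 6.1.2. State that the figure compared with 60% is the glucose-criteria success rate among sets without a 6.1.3 device failure.
2. In 7.3, define *function* for the daily proportion as no 6.1.2 failure (infection signs and occlusion alarm included) and no 6.1.3 device failure. The endpoint can then still serve for safety.
3. Report the 5.4 comparisons both with infection-only removals counted as failures and without, and name the main one before data are seen.
4. As a safeguard, state in 7.2 that a set removed for a recorded device failure is non-functioning from that day and is not subject to last observation carried forward.
5. Reconcile the completion wording. For Week 2, sections 1.4.1 and 2.9 both refer to an infusion set failure. For Week 3, 1.4.1 keeps that term while 2.9 refers to a device issue.

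The cost is protocol wording only, since 6.1.4 already collects both failure types. The downside is that the reported Achilles proportion may be less favourable.

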After insertion of the Achilles infusion set at the study site, participants will be required to manage routine basal/bolus insulin therapy using study specific supplies only with their current insulin pump during two extended wear home use periods of up to 7 days each (*Week 2* and *Week 3*, respectively). Participants will monitor BG levels with Dexcom G5 CGM device to avoid glycemic excursions. Participants will conduct daily visual inspection and record Achilles insertion set location pain levels and skin reactions. If subject experiences an Achilles infusion set device issue, participants shall insert a commercial CSII set to maintain routine insulin therapy. Participants will be provided with training and written instructions if an Achilles device issue occurs at any time during home wear periods. They are instructed to contact study staff as early as possible after infusion set failure. *Week 2* evaluation period is complete when either, 1) an Achilles infusion set failure occurs and subject needs to insert a commercial CSII set to maintain routine therapy until they return to the study center, or 2) subject has worn Achilles for the total 7-day wear period.

Upon completion of *Week 2* wear period (either after full 7 days or earlier), participants are asked to return to study center. Data will be downloaded from the subject's insulin pump, ketone monitors and CGM. Patient Diaries will be collected after each wear period. All study supplies will be replenished as needed.

Week 3 evaluation begins when study center inserts another Achilles infusion set (Day 0c). Participants will maintain insulin pump therapy per standard of care. *Week 3* home use evaluation is considered complete when, 1) an Achilles device issue requires subject to insert a commercial CSII set; or 2) subject has worn Achilles for a second total 7 -day wear period.

Participants who do not participate in *Week 3* will exit the study at time of declination. All data up the point of study exit will be documented and included for analysis. Participants may exit the study at any time without prejudice to their ongoing medical care. The time and reason for early exit will be recorded, and all data up to the point of study exit shall be documented and included for analysis.

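### A set removed early for suspected non-delivery can meet no infusion set failure criterion, and carry-forward then scores it as functioning to Day 7

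*Combined protocol and SAP*

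**What the plan says.** **Failure criteria.** Sections 1.4.1 and 6.1.2 (Primary Endpoint) give the same four items. The first is unexplained glucose above 250 mg/dL, more than two hours after a meal, that is "not responsive to a pump bolus dose where response to the bolus is defined as a fall of at least 50 mg/dL" within one hour. The second is glucose above 250 mg/dL "not associated with acute intercurrent illness, but with a concurrent ketone level ≥ 0.6 mmol/L". The other two are signs of infection and "occurrence of a non-resolvable insulin pump occlusion alarm signal". A NOTE in 6.1.2 confines the cannula function criteria to "hyperglycemic episodes that participants recognize and attempt to correct with an insulin bolus or document with ketone elevation".

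**Mechanical failure.** For the insulin weeks, dislodgement and other device malfunction are in the secondary endpoint (6.1.3). Section 6.1.4 lists a count of failures under both 6.1.2 and 6.1.3.

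**End of wear.** Sections 1.4.1 and 2.9 tell participants to switch to a commercial set for a *device issue*, a term that is not defined. Section 1.4.1 ends both Week 2 and Week 3 on an infusion set failure or at 7 days. Section 2.9 says the same for Week 2, but ends Week 3 when "an Achilles device issue requires subject to insert a commercial CSII set" or at 7 days.

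**Analysis.** Section 7.3 makes the primary quantity the daily proportion of sets that function, up to 7 days, and does not define *function*. Section 7.2 prescribes last observation carried forward for participants who do not complete the interval. Section 5.4 sets benchmarks of 30% of all sets, and 60% of sets without mechanical malfunction. It describes adequate performance in the cited study as freedom from early mechanical failure and "no episodes of uncorrectable hyperglycemia prior to the end of 7 days of infusion set wear time". Success means exceeding these figures; no interval or test is attached.

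**The concern.** The events that can end a wear are broader than the events that count as a failure. A participant who sees high glucose, suspects the set and changes it straight away has given the set no chance to show bolus non-response. If ketones are below 0.6 mmol/L, or not measured, and there is no alarm or infection sign, no criterion is met. The same applies when the set is changed before the one-hour response window has closed. Such sets were taken out because delivery was doubted, so some of them are likely to be true failures, and none of them gave seven days of wear.

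Early replacement is foreseeable. Eligibility excludes people who routinely wear a set longer than 3.5 days, section 4.2 describes patients as used to frequent changes, and section 4.4 makes a commercial set available at any time. The success rule is a bare comparison of proportions in a small sample, so the scoring of one or two sets can decide it.

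**Working it through.** **Step 1. Follow one set through the criteria.** Take a Week 2 set removed on Day 4 for suspected non-delivery, before one hour has passed since any bolus.
- Bolus non-response: not assessable, so not met.
- Ketone ≥0.6 mmol/L: not met if the value is lower or was not taken.
- Non-resolvable occlusion alarm: not met if none occurred.
- Infection sign: not met if none was seen.
- Dislodgement or malfunction: if present, it counts under 6.1.3 but not under 6.1.2.

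The set has ended early with no failure under the primary definition.

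**Step 2. Follow it through the analysis.** Under 1.4.1 the week is complete only on a failure or after 7 days. This week is neither, so the interval is incomplete. The one rule for that case is carry-forward (7.2), and the last recorded status is functioning. The set is therefore scored as functioning on Days 5 to 7. If 2.9 is used for Week 3, the interval is complete on a *device issue*, and no scoring rule is given at all. The per-protocol sensitivity analysis cannot reveal the problem, because that population takes in anyone who completed any part of the wear period.

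**Step 3. Effect on the count.** The plan has no calculated figure to reproduce; section 5.3 says the sample size was chosen by reference to similar studies. Assume 20 participants (6.2.6) × 2 insulin periods = 40 sets. Each set is 1/40 = 2.5 percentage points. Exceeding 30% needs at least 13 sets, since 12/40 is exactly 30.0%.

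| True successes | Unclassified sets | Scored as not functioning | Carried forward | Excluded |
|---|---|---|---|---|
| 12 | 1 | 12/40 = 30.0% | 13/40 = 32.5% | 12/39 = 30.8% |
| 12 | 4 | 12/40 = 30.0% | 16/40 = 40.0% | 12/36 = 33.3% |
| 24 | 1 | 24/40 = 60.0% | 25/40 = 62.5% | 24/39 = 61.5% |

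The last row is for the 60% benchmark. Its denominator is sets without mechanical malfunction, so 40 is an upper limit there.

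**Step 4. Effect on the chance of passing (illustration).** Let p be the true success proportion and m the share of true failures left uncounted and carried forward. The apparent proportion is a = p + (1 − p)m. The chance of passing is P(X ≥ 13) with X ~ Binomial(40, a), taking the two sets per participant as independent. With p = 0.30:

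| m | a | P(exceeds 30%) |
|---|---|---|
| 0 | 0.300 | 0.42 |
| 5% | 0.30 + 0.70 × 0.05 = 0.335 | 0.61 |
| 10% | 0.30 + 0.70 × 0.10 = 0.370 | 0.77 |
| 20% | 0.30 + 0.70 × 0.20 = 0.440 | 0.95 |

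Against 60% with p = 0.60 (at least 25 of 40), the same four values of m give 0.44, 0.54, 0.65 and 0.82. The documents give no value for m; the range is an assumption.

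**The case against.** A reader might infer that a set replaced without a pump bolus or raised ketone is never a failure. The documents do not support that. An occlusion alarm bears directly on non-delivery and counts without either, as do infection signs. Dislodgement and malfunction count under 6.1.3 whether or not glucose is uncontrolled. Willingness to test ketones above 250 mg/dL is an inclusion criterion, and meters and strips are supplied, which narrows the gap. It does not close it: a reading below 0.6 mmol/L leaves the set unclassified.

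A reader might also infer that the bolus wording inflates the success proportion by itself. It does not. A set removed on Day 3 is not naturally read as functioning on Day 4, and if it is scored as not functioning there is no inflation. The upward shift comes from carry-forward, or from exclusion. That objection limits the claim, but 7.3 states no such scoring and 7.2 states carry-forward.

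Nor do the documents consistently end Weeks 2 and 3 on different events. The contrast appears only in 2.9; section 1.4.1 ends both on a failure.

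The strongest remaining objection concerns comparability. The study is meant to resemble other infusion set studies (6.1.1), and the documents do not show how the cited study scored pre-emptive changes. Widening failure for Achilles alone could make the comparison less like-for-like, and some sets changed pre-emptively will have been working. This stands, and is the reason to keep the strict definition as a sensitivity analysis. Pump prime events and return or explant dates are already collected, so early removals can be dated; what is missing is the rule for scoring them.

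**Conclusion.** The concern holds in a limited form. In Weeks 2 and 3, a set removed early for suspected non-delivery that triggers none of the four listed criteria is not an infusion set failure, and a mechanical failure counts only under the secondary endpoint, although the 30% benchmark includes it. Applied as written, 7.2 then scores such a set as functioning to Day 7, while 5.4 looks to the end of 7 days of wear. How many sets this affects cannot be derived from the documents. Assuming 40 insulin sets, each adds 2.5 points under carry-forward, and one is enough to move 12/40 to 13/40 and pass the 30% benchmark; excluding it (12/39) also passes. The probabilities rest further on the assumed share m and on independence of the two sets per participant. This is a first-in-human feasibility study without a hypothesis test, but it has a pass rule that one set can flip, so the scoring should be settled before data are analysed.

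**What to change.** - In 6.1.2 and 7.3, define Day-7 success for the 5.4 comparison as the same set in place and in use at the end of 7 days with no failure criterion met.
- Score any earlier removal or replacement prompted by suspected under-delivery, unexplained high glucose or a device issue as not functioning from that day, whether or not a bolus response or ketone value was recorded.
- In 7.2, do not carry a functioning status forward for these sets. Censor ends of wear for unrelated reasons, such as withdrawal.
- Report the strict criteria-only definition as a sensitivity analysis.
- Record the reason for removal on the case report form.
- Reconcile *device issue* (2.9) with *infusion set failure* (1.4.1, 6.1.2) as the end-of-wear term.

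The cost is wording in four or five sections and one added form field. What participants are told to do does not change. The downside is a slightly less favourable success figure, with some working sets scored as not functioning; the sensitivity analysis shows how much that matters.

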6.1.4 Variables to Assess

The variables assessed in this study include:

- Frequency of pump prime events (i.e infusion set change out) as evaluated from the 14d pump data downloaded during the screening visit as well as during the evaluation periods

- Interstitial glucose values as measured by the CGM, downloaded at each visit to the study center
- Capillary blood glucose values measured by fingerstick measurements, downloaded from the glucose meter/recorded in Patient Diary
- Ketone values measured by fingerstick measurements, downloaded from the ketone meter/recorded in Patient Diary
- Daily pain assessments from the VAS recorded in Patient Diary
- Number of Achilles infusion set failures per definition in sections 6.1.2 and 6.1.3
- Number of hyperglycemic events (CGM, Patient Diary)
- Number of hypoglycemic events (CGM, Patient Diary)

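### Glucose-based set failures count only if the participant recognizes and acts on the episode, so missed episodes raise the success rate compared with 30% and 60%; a sensitivity range from existing downloads is needed

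*Combined protocol and SAP*

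**What the plan says.** Section 6.1.2 Primary Endpoint defines insulin delivery in Weeks 2 and 3 "as evidenced by the absence of uncontrolled hyperglycemia/suspected occlusion". There are two glucose criteria, both starting from a reading above 250 mg/dL:

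- The first applies more than 2 hours after a meal and requires an episode "not responsive to a pump bolus dose where response to the bolus is defined as a fall of at least 50 mg/dL" within one hour.
- The second requires an episode "not associated with acute intercurrent illness, but with a concurrent ketone level ≥ 0.6 mmol/L".

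Infection signs and a non-resolvable occlusion alarm are listed separately as other evidence of failure. The NOTE below them says: "Cannula function criteria refer to hyperglycemic episodes that participants recognize and attempt to correct with an insulin bolus or document with ketone elevation". Section 6.1.3 points back to this NOTE. The synopsis (1.4.1) lists the same four failure routes without it.

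The relevant data are collected. Section 6.1.4 lists "Interstitial glucose values as measured by the CGM, downloaded at each visit to the study center", and 2.9 says after Week 2: "Data will be downloaded from the subject's insulin pump, ketone monitors and CGM". Section 6.1.4 also counts hyperglycemic events from CGM and diary, but as a separate variable not linked to set failure.

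Section 7.3 states: "The primary study endpoint is the proportion of Achilles infusion sets that function each day of use, up to 7 days". Section 7 has no rule for checking the downloads against the failure criteria and no adjudication of set function. Section 5.4 cites 30% of sets adequate to day 7, and 60% among sets without mechanical malfunction, and adds: "Success criteria will be considered met if the Achilles infusion set exceeds these performance outcomes".

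**The concern.** Success is the absence of a qualifying event, and under the NOTE a glucose event qualifies only through something the participant does. The first criterion cannot be evaluated without a bolus, nor the second without a ketone test. An episode that is slept through or left untreated and untested therefore leaves the set counted as functioning, unless an infection sign or an occlusion alarm appears. No sentence says this outright. It follows from the absence-based endpoint and from the lack of any overriding rule in section 7.

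The study is single-arm and open, and success is judged against fixed historical rates with no confidence bound. No concurrent control shares the same under-counting. Because the synopsis omits the restriction, two analysts could also score the same set differently.

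**Working it through.** The plan gives no power or sample-size calculation (5.3 states there is no definitive hypothesis), so there is no figure of its own to reproduce. What follows only shows scale.

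**Inputs from the documents**
- 20 participants (6.2.6) with up to two insulin-carrying sets each (Weeks 2 and 3), so up to 40 sets.
- Benchmarks of 30% overall and 60% among sets without mechanical malfunction (5.4).
- The success rule is to exceed the benchmarks (5.4). With 40 sets, exceeding 30% means at least 13 and exceeding 60% means at least 25.

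**Assumptions, not in the documents**
- m is the share of sets failing on glucose grounds whose failure is never recognized during the wear period. Shown for 0, 10%, 20% and 30%.
- Sets are independent. Two sets from one person are correlated, so the probabilities are approximate.
- The two benchmark rates share one denominator.

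**Step 1: how much failure is glucose-based.** If a share s of sets has no mechanical malfunction and 60% of those are adequate, then 0.60 × s = 0.30, so s = 0.50. Mechanical failures are 0.50 and glucose failures are 0.50 × 0.40 = 0.20. Only these 20 points can be hidden by the NOTE.

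**Step 2: the 30% benchmark.** Observed success = 0.30 + 0.20m. Exact binomial, P(at least 13 of 40):

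| m | Observed rate | P(exceed 30%) |
|---|---|---|
| 0 | 30% | 0.42 |
| 10% | 32% | 0.53 |
| 20% | 34% | 0.64 |
| 30% | 36% | 0.73 |

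**Step 3: the 60% benchmark.** Here all failures are glucose-based, so observed success = 0.60 + 0.40m. Fewer than 40 sets would enter. By step 1 it would be about 20 (0.50 × 40), where exceeding 60% means at least 13.

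| m | Observed rate | P(exceed 60%), 40 sets | P(exceed 60%), 20 sets |
|---|---|---|---|
| 0 | 60% | 0.44 | 0.42 |
| 10% | 64% | 0.65 | 0.56 |
| 20% | 68% | 0.82 | 0.71 |
| 30% | 72% | 0.93 | 0.83 |

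**Step 4: what m means.** It refers to a set's whole wear period, not to one episode. If 30% of episodes were missed independently and a failing set produced three, all three would be missed with probability 0.30 × 0.30 × 0.30 = 0.027, or about 3%. A single missed episode mostly delays the recorded failure day. That still affects the day-by-day proportion in 7.3, but not the day-7 result.

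**The case against.** The strongest reply is that few failures would be missed. Section 4.4 has CGM alarms engaged throughout and staff texted on alarm, participants agree to test ketones above 250 mg/dL (inclusion criterion 8), and a failing set that stays in use is likely to produce further episodes. This stands: nothing in the documents supports m of 20% or 30%. But an alert does not become a scored failure unless the participant then boluses or tests.

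A second reply is that the benchmark study may have counted episodes the same way, in which case much of the bias would cancel. The documents do not describe its ascertainment, so this can be neither assumed nor dismissed. It is a good reason to keep the current definition as the main result.

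Third, CGM episodes are already a secondary endpoint and 7.7 promises listings by patient and time point. A reader could cross-check them, but only informally and after seeing the results.

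Fourth, downloads cannot show non-response where no bolus was given, or ketones where none were measured. A rule that needs a logged bolus will mostly find again the episodes the NOTE already covers. This also stands, and is why untreated excursions need their own category.

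A reader might infer that any failing set can be hidden, so that observed success is 0.30 + 0.70m (37%, 44% and 51%). The documents do not support this. The NOTE concerns the two hyperglycemia criteria only; infection signs and occlusion alarms are separate routes, and a dislodged or kinked set is not concealed by an ignored glucose reading.

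A reader might also infer that every scoring error favours the device. That is too strong. No minimum correction bolus is set, so a small bolus followed by a fall under 50 mg/dL scores as failure, and erythema above 1 cm counts as failure whatever the delivery.

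**Conclusion.** The point holds as a one-directional gap in ascertaining glucose-based failures, together with an inconsistency between 1.4.1 and 6.1.2. Missed glucose episodes can only raise the observed success rate; by how much is unknown. Under the stated assumptions (independent sets, one denominator, m of 10% to 30%) the overall rate rises by 2 to 6 points, and the chance that a device truly at 30% exceeds 30% goes from 0.42 to between 0.53 and 0.73. The effect on the 60% comparison is larger, because every failure there is glucose-based.

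It does not follow that missed episodes alone would produce a declared success. Section 5.4 refers to both outcomes, m is probably low, and the benchmark may share the rule. The 0.42 and 0.44 at m = 0 come from comparing a point estimate with a fixed rate without a confidence bound, which is a separate matter.

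**What to change.** 1. Reconcile the failure definition in 1.4.1 with the NOTE in 6.1.2, so that one rule governs what counts as a glucose-based failure.
2. Keep the participant-recognized definition as the main result, to stay as close as possible to the benchmark.
3. In section 7, pre-specify one sensitivity analysis that applies the existing glucose and ketone criteria to all CGM, pump and ketone-meter downloads, whether or not the participant reported the episode. State that the same downloads are taken after Week 3; 2.9 describes the combined download only after Week 2.
4. List separately, as possible failures, sustained CGM excursions above 250 mg/dL more than 2 hours after a meal bolus with no correction bolus or ketone test. Define sustained in advance. Counting these as failures gives a lower bound on success.
5. Report the main result and the lower bound as a range beside the 5.4 benchmarks. Do not make the lower bound a success requirement, because that would apply a stricter count to this device than may have been applied to the benchmark.

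The cost is analysis-plan wording and modest programming. No new visits, measurements or changes to participant care are needed. The downside is that some flags will be sensor error or excursions unrelated to the set (HbA1c up to 8.5% is allowed), so the lower bound may be conservative and the reported success less favourable.
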